## 5.5 Modified Intent-to-Treat (mITT) Population

The mITT population will consist of all randomized subjects who received at least one dose of randomized study treatment and who have sufficient data to assess the primary efficacy endpoint. Subjects who withdraw early for reasons unrelated to treatment success or failure will be excluded. Withdrawals for escalation failure, treatment-related AEs and deaths, or the addition of *ad libitum* peanut consumption to diet will not be excluded. Exclusions will be determined by blinded review prior to database lock and unblinding. Subjects will be analyzed according to randomized treatment. The mITT population will be used for sensitivity and supportive analyses of the primary and key secondary efficacy endpoints.

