## 5.6 Per Protocol (PP) Population

The PP population will be a subset of the mITT population, limited to subjects who have no major protocol deviations that may influence the desensitization response. With the exception of withdrawals for escalation failure and treatment-related AEs and deaths, all subjects who withdraw prematurely or have a major protocol deviation will be excluded from the PP population. Exclusions will be determined by blinded review prior to database lock and unblinding. Subjects will be analyzed according to randomized treatment. The PP population will be used for sensitivity and supportive analyses of the primary and key secondary efficacy endpoints.

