#### 7.3 Maximum Tolerated Dose at DBPCFCs and Escalation Failures

The MTD for a DBPCFC is defined as the maximum single dose of peanut protein resulting in no more than mild symptoms and assessed by the investigator to have been tolerated (i.e., subject did not experience any dose-limiting symptoms). The MTD at the Screening DBPCFC will be used as the baseline amount of peanut protein tolerated. If a subject is administered non-standard doses at DBPCFC (i.e., other than the doses listed in Tables 3.1 or 3.4), the MTD will be considered the highest tolerated standard dose (i.e., 3 mg, 10 mg, 30 mg, 100 mg for either DBPCFC; 300 mg for Exit DBPCFC) which is tolerated.

An escalation failure is a subject who does not reach the target 300 mg/day dose by Week 34, or fails to complete at least a 2-week maintenance at that dose level.

Where necessary, desensitization response and MTD at the Exit DBPCFC will be imputed for subjects who do not have an Exit DBPCFC as shown in Table 7.1. As a general rule, subjects who do not undergo an Exit DBPCFC for any reason will be categorized as desensitization non-responders; and the imputed value for their MTD will be the maximum dose of peanut protein they tolerated in their Screening DBPCFC. The one exception to this rule is in the event of documentation that a subject introduced ad libitum peanut consumption into their diet and tolerated amounts of peanut exceeding a single peanut kernel (the targeted level of desensitization in the study). Although subjects are repeatedly and strenuously admonished, per protocol, to maintain a peanut-avoidant diet, there is always the potential for the admonishments to go unheeded, as well as for accidental exposure. In the unlikely event that a subject starts to consume peanut ad libitum before exiting the trial, whether or not this occurs as the result of a protocol violation, provision has been made for imputing their results (see Table 7.1). If, however, the amount of peanut consumed and tolerated by a subject claiming ad *libitum* peanut consumption cannot be ascertained from the eCRF or source documentation, then the subject will be classified as a non-responder who missed their Exit DBPCFC after having discontinued for reasons unrelated to treatment. If a subject added ad libitum peanut consumption to their diet and had additional reasons for missing the Exit DBPCFC, then the imputation rules for ad libitum

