[3] More than one reason for discontinuation may be given. Each discontinuation reason will be classified as treatment-related, or not, during blinded data review. Escalation failure is a specific reason for early discontinuation on the eCRF.

[4] Information from free text fields on the eCRF for protocol deviations or reason for early discontinuation will be used to determine the imputed value. If it is clear that an amount of peanut exceeding a single peanut kernel was regularly consumed without eliciting symptoms, then a value of 300 mg will be imputed. If the amount of peanut consumed cannot be ascertained or is less than the equivalent of a peanut kernel, then the subject will be classified as a Non-responder and no value will be imputed.

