## 7.4 Classification of Responder Status

A desensitization responder is defined as a subject who achieves a desensitization response as determined by tolerating at least 300 mg (443 mg cumulative) of peanut protein (measured as 600 mg of peanut flour) at the Exit DBPCFC with no more than mild symptoms.

A non-responder is an escalation failure or a subject who experienced dose-limiting symptoms (moderate or worse) at or before the 300 mg dose of peanut protein during the Exit DBPCFC.

Additional classification of responder and non-responder categories are provided in Table 7.2.

Response	Response	Criteria	
Category	Subcategory [1]		
Desensitization Responder	Passed Exit DBPCFC	Tolerate at least 300 mg (443 mg cumulative) of peanut protein at the Exit DBPCFC with no more than mild symptoms	
	Ad libitum peanut consumption	Added ad libitum peanut consumption to their diet	
Non-Responder	Failed Exit DBPCFC	Fail to tolerate at least 300 mg (443 mg cumulative) of peanut protein at the Exit DBPCFC with no more than mild symptoms	
Reached 300 Reason		Reasons [2] include:	
	mg/day but Exit DBPCFC was not conducted	
 
Eligible for DBPCFC but it was not conducted due to at least one treatment-related reason, as entered on the eCRF
 
Eligible for DBPCFC but it was not conducted
 
	
		only for reasons unrelated to treatment, as entered on the eCRF	
	Escalation Failure	Fail to achieve the target maintenance study product dose of at least 300 mg and thus did not qualify for the Exit DBPCFC. Reasons[3] include:	
		
 
Discontinued as an escalation failure during initial escalation (Visit 01)
 
	
		
 
Discontinued as an escalation failure during up- dosing prior to Week 24
 
	
		
 
Discontinued as an escalation failure after Week 24
 
	
		Discontinued for treatment-related AE or death	
		
 
Discontinued for other reasons related to treatment
 
	
		Discontinued for reasons unrelated to treatment	

Table 7.2 Response Categories

[1] Subjects will be assigned to only one response subcategory during blinded data review.

[2] More than one reason may be given for the DBPCFC not being conducted for a subject who reached the 300 mg/day target. Each reason will be classified as treatment-related, or not, during blinded data review.

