## 9.2 Additional Analyses of the Primary Efficacy Endpoint

The Exit DBPCFC is defined as indeterminate if the subject was not able to tolerate the placebo challenge up to and including a dose of 600 mg (1043 mg cumulative). Also, prior to Protocol Amendment 3, subjects could be enrolled if they had an indeterminate Screening DBPCFC. The Screening DBPCFC will be considered indeterminate if the subject is not able to tolerate a dose of 100 mg (443 mg cumulative) of the placebo challenge. Subjects with an indeterminate DBPCFC (either at screening or exit) will be excluded for a sensitivity analysis of the primary efficacy analysis in this ITT subset.

The primary efficacy analysis will also be repeated in the mITT and PP populations as sensitivity analyses. These sensitivity analyses effectively assess the results by treating truly missing data as missing-at-random rather than by imputing a response.

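### The per-protocol rule in SAP 5.6 drops non-responders who stopped for treatment-related reasons other than an adverse event, death or escalation failure, and they are not missing at random

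*SAP*

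**What the plan says.** **mITT (SAP 5.5).** "Subjects who withdraw early for reasons unrelated to treatment success or failure will be excluded. Withdrawals for escalation failure, treatment-related AEs and deaths" are the two sides of the rule. The second group is kept, as are subjects who added peanut to their diet.

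**PP (SAP 5.6).** PP is a subset of mITT. The rule on leavers begins: "With the exception of withdrawals for escalation failure and treatment-related AEs and deaths, all subjects who withdraw prematurely". Those subjects are removed, and so are subjects with a major deviation. SAP 5.5 and 5.6 give both sets the same job: sensitivity and supportive analyses of the primary and key secondary endpoints.

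**Reasons for not reaching the challenge (SAP 7.4, Table 7.2).** The Escalation Failure row itemises reasons. "Discontinued for other reasons related to treatment" has its own line, apart from treatment-related AE or death. "Discontinued for reasons unrelated to treatment" is another line in the same row.

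**Two meanings of one term.** SAP 7.3 defines escalation failure by outcome: "An escalation failure is a subject who does not reach the target 300 mg/day dose by Week 34, or fails to complete" the two weeks at that dose. Footnote [3] to Tables 7.1 and 7.2 uses it as a reason: "Escalation failure is a specific reason for early discontinuation on the eCRF". Sections 5.5 and 5.6 do not say which applies.

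**Purpose (SAP 9.2).** Of the mITT and PP analyses it says: "These sensitivity analyses effectively assess the results by treating truly missing data as missing-at-random rather than by imputing a response".

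**The concern.** A sensitivity analysis that treats missing outcomes as missing at random should set aside only subjects whose absence tells us nothing about treatment. Someone who stops because of the treatment, without a recorded AE and without escalation failure as the eCRF reason, is a treatment failure. ITT counts that subject as a non-responder. The mITT exclusion does not reach the subject either, because it covers only unrelated reasons. The PP exceptions do not name the subject, so PP drops them.

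Such cases are possible. Protocol 7.1 sends allergic dosing symptoms to the dosing form, so a withdrawal over them need not carry an AE record. If these withdrawals are commoner on CPNA, PP takes failures out of the CPNA denominator and makes the result look better than ITT. PP would then seem to confirm the primary result when part of the agreement comes from the exclusion rule.

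**Working it through.** **1. The plan's own figures.** SAP section 4 takes 25 per arm and counts subjects without an Exit DBPCFC as non-responders.

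- 3 missing per arm: placebo 25% × 22/25 = 22%; CPNA 66.7% × 0.88 = 58.7%.
- 5 missing per arm: placebo 25% × 20/25 = 20%; CPNA 70.75% × 0.80 = 56.6%.
- Exact enumeration of the uncorrected Pearson chi-square test (two-sided 0.05) gives power of 80.0% and 80.2%. The stated 80% is reproduced.

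These are ITT figures, and the population rules in 5.5 and 5.6 do not touch them.

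**2. The rules side by side.** Narrow means the eCRF reason (footnote [3]). Broad means the outcome definition in 7.3.

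| Subject without an Exit DBPCFC | mITT, narrow | PP, narrow | PP, broad |
|---|---|---|---|
| eCRF reason is escalation failure | kept | kept | kept |
| Stopped for a treatment-related AE | kept | kept | kept |
| Stopped before 300 mg/day for another treatment-related reason | not excluded | **dropped** | kept |
| Reached 300 mg/day, challenge missed for a treatment-related, non-AE reason | not excluded | **dropped if this counts as premature withdrawal** | **same** |
| Left before 300 mg/day, every reason unrelated | excluded | excluded | depends on which sentence of 5.5 prevails |

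The bold cells are the defect. On the narrow reading the mITT column is consistent and fits 9.2, but the PP column is not and does not.

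**3. Size for the response rate (assumed counts).** Let x of n CPNA subjects respond and let PP drop k CPNA failures, with placebo unchanged. The CPNA rate goes from x/n to x/(n − k).

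- x = 15, n = 25, k = 3: 60.0% becomes 15/22 = 68.2%, a gain of 8.2 points.
- x = 14, n = 25, placebo 5/25 = 20%: the difference is 56.0 − 20.0 = 36.0 points. With k = 3 it is 63.6 − 20.0 = 43.6. With k = 5 it is 70.0 − 20.0 = 50.0.
- Borderline case: 11/25 versus 5/25 gives chi-square p = 0.069. With k = 2, 11/23 versus 5/25 gives p = 0.041.

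**4. Size for the change in MTD.** SAP 7.3 imputes the screening MTD to these subjects, so their log10 change is 0. Dropping three of 25 leaves the sum of changes as it was. The unadjusted CPNA mean change is multiplied by 25/22 = 1.14.

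**5. What the choice of meaning could do to mITT.** Assume every subject without a challenge left for unrelated reasons. With 3 per arm, the difference is 58.7 − 22 = 36.7 points if they are kept and 66.7 − 25 = 41.7 if they are excluded. With 5 per arm it is 56.6 − 20 = 36.6 or 70.75 − 25 = 45.75. These gaps are upper bounds, because section 4 also counts subjects who miss the dose target for other reasons.

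**The case against.** **The mITT rule contradicts itself.** A reader might infer this by putting the 7.3 definition into 5.5: a subject who moves away at Week 10 would be excluded by one sentence and kept by the next. The documents do not force that reading. Section 5.5 speaks of withdrawing for escalation failure, which is a reason, and footnote [3] says it is a specific eCRF reason. Tables 7.1 and 7.2 list discontinuation as an escalation failure apart from discontinuation for unrelated reasons, and 9.2 fits this meaning. What remains is a term that 5.5 and 5.6 should define. Even on the broad reading mITT is not simply ITT, because eligible subjects left unchallenged only for unrelated reasons can still drop out of it.

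**The PP gap closes on the broad reading.** This is true for subjects who stopped before 300 mg/day. But it is the narrow reading that makes 5.5 work, and the two sections should use the term in one sense. The subject who reached 300 mg/day and missed the challenge is exposed on either reading.

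**The group is small.** This largely stands. Protocol 7.6 lists home symptom logs as a source of AEs, SAP 10.3 has AE periods for Visit 01 and up-dosing visits, and the addendum (2.1) classifies AEs as allergic symptoms. Repeated failed up-dosing is itself escalation failure under the protocol. Only treatment-related stops outside all of these remain.

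**Blinded review will sort it out.** It can settle an undefined term. It cannot properly keep subjects whom 5.6 tells it to remove. Several reasons per subject are allowed, and neither 5.5 nor 5.6 gives a precedence rule. Masking limits selective use of that gap, but the reviewers do see challenge results and responder class (SAP section 12, Table 11.1).

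**Conclusion.** The point holds for PP. On the reading that makes 5.5 coherent, 5.6 removes informative non-responders whom mITT keeps, which conflicts with the purpose stated in 9.2. It should be corrected before database lock, but it does not threaten the trial's main result.

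The size depends on how many such withdrawals occur and in which arm. With the assumed counts, three dropped CPNA failures add about 8 points to the CPNA rate. A reader might infer that these failures fall mainly on CPNA. SAP 7.7 treats dosing symptoms as suggestive of assignment, so that is plausible, but the documents give no split by arm and the plan's scenarios have equal numbers missing in each. If the split were even, the shift in the difference would be smaller.

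Two wider conclusions are not supported. The primary and key secondary analyses use ITT, where these subjects already count as non-responders with their screening MTD, so neither those results nor the power changes. The addendum's Completer set (2.2) is drawn from mITT but requires eligibility for the Exit DBPCFC. Subjects who never qualified are outside it on any reading, so it is barely affected.

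**What to change.** 1. In SAP 5.6, add to the retained list any withdrawal, or missed Exit DBPCFC, with at least one treatment-related reason. Only subjects whose every reason is unrelated to treatment are then excluded on withdrawal grounds. This also supplies the missing rule for multiple reasons. Major-deviation exclusions stay as they are, so PP remains distinct from mITT.
2. In SAP 5.5 and 5.6, state that escalation failure there means the eCRF discontinuation reason or a protocol-mandated halt of up-dosing, not the wider outcome definition in 7.3.

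The cost is a few lines of SAP text before lock. No new data are needed, because the footnotes to Tables 7.1 and 7.2 already have each reason classified as treatment-related or not at the blinded review. The downside is that the CPNA response rate in PP may look slightly less favourable.

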## 5.6 Per Protocol (PP) Population

The PP population will be a subset of the mITT population, limited to subjects who have no major protocol deviations that may influence the desensitization response. With the exception of withdrawals for escalation failure and treatment-related AEs and deaths, all subjects who withdraw prematurely or have a major protocol deviation will be excluded from the PP population. Exclusions will be determined by blinded review prior to database lock and unblinding. Subjects will be analyzed according to randomized treatment. The PP population will be used for sensitivity and supportive analyses of the primary and key secondary efficacy endpoints.

#### 5.7 Screening DBPCFC Only Population

The Screening DBPCFC Only population will consist of all subjects who underwent at least one part (peanut flour challenge or oat flour challenge) of the Screening DBPCFC, but did not receive any randomized study treatment.

## **6** CONSIDERATIONS FOR DATA ANALYSIS

#### 6.1 Programming Environment

SAS® version 9.2 or higher will be used for statistical analyses and to produce tables, listings, and figures (if applicable).

#### 6.2 Strata and Covariates

Demographic and baseline characteristics are evaluated by baseline peanut IgE level and baseline SPT wheal diameter, as described in Section 8.6. In addition, exploratory efficacy analyses will be used to evaluate the effect of baseline factors on peanut MTD at Exit DBPCFC and the change in peanut MTD, as described in Sections 9.5.1 and 9.5.2.

## 6.3 Subgroups

Demographic and baseline characteristics will be presented by baseline IgE level, as described in Section 8.6. There are no other planned subgroup analyses.

## 6.4 Multiple Comparisons and Multiplicity

The key secondary endpoints are tested in a hierarchical method, as described in Section 9.3. No other adjustments will be made for multiple comparisons.

## 6.5 Significance Level

Unless stated otherwise, all statistical tests will be two-sided, with a significance level of 0.05. Confidence intervals (CIs) will be calculated at the 95% level, reflecting a type I error rate of 0.05.

## 6.6 Statistical Notation and Methodology

Unless stated otherwise, the term "descriptive statistics" refers to the number of subjects (n), mean, median, standard deviation, minimum, and maximum for continuous data and frequencies and percentages for categorical data. Unless noted otherwise, the denominator for percentages will use the number of subjects in the analysis population. Minimum and maximum values will be rounded to the precision of the original value, means, medians, first quartiles, and third quartiles will be rounded to 1 decimal place greater than the precision of the original value, standard deviations will be rounded to 2 decimal places greater than the precision of the original value. Percentages will be rounded to the nearest whole number (zeros are not displayed) with values of "<1%" and ">99%" shown as necessary for values falling near the boundaries.

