## 9.3.1 Maximum Tolerated Dose at Exit DBPCFC

The Exit DBPCFC uses a modified PRACTALL dosing regimen. PRACTALL doses are approximately on a logarithmic scale (3 mg, 10 mg, 30 mg, 100 mg, 300 mg). The highest dose level, 600 mg, was chosen in lieu of the 1000 mg dose level from the PRACTALL guidance to further insure safety. Each single PRACTALL dose step corresponds to a 3 to 3.33-fold (roughly 3.16-fold) increase in dose or a 0.477 to 0.523 (roughly 0.5) increase in the log10 scale. The 600 mg dose level is 2-fold increase in dose or approximately a 0.3 increase in the log10 scale above the 300 mg dose. Each increase of 2 PRACTALL dose steps (e.g. 30 to 300 mg or 10 to 100 mg) corresponds to a 10-fold increase in dose or an increase of 1 unit in the log10 scale. Subjects that cannot tolerate the lowest Exit DBPCFC dose will be set to 0.3 mg (a 1 unit decrease from the 3 mg dose, on the log10 scale) for purposes of analysis to allow for the logarithmic transformation. The MTD for the Exit DBPCFC will be imputed using the rules in Section 7.3 for all subjects with a missing Exit DBPCFC.

Estimates for the probability of tolerating each dose or higher will be based on the discrete hazards model with terms for treatment group effect and the MTD at the Screening DBPCFC (baseline) in the log10 scale. The extreme value hazard function will be used for the model. The probability estimates will be tabulated by treatment group and adjusted for the MTD at baseline. The adjusted probability estimates will be calculated at the median of the MTD at baseline. The adjusted probability estimates will also be plotted. An unadjusted probability estimate will also be calculated by removing the MTD at baseline term from the model. All subjects in the analysis population are considered eligible for the 1 mg dose. Subjects who did not receive the optional 1 mg dose at the Exit DBPCFC will be considered to have successfully passed that dose level and be eligible for the 3 mg dose level.

The treatment group effect will be assessed using the model with both terms to adjust for the MTD at baseline. The hazard ratio for the treatment group effect with its 95% confidence interval and the p-value will be based on the Wald statistic.

The maximum symptom severity at each dose level, and the cumulative maximum severity at each dose level, will be summarized by treatment group.

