Listings will be provided for all adverse events; serious adverse events (SAEs); severe, life-threatening, or fatal adverse events; adverse events leading to death; adverse events leading to permanent withdrawal of study treatment; adverse events related to study treatment; and adverse events occurring within 2 hours of the last dose of randomized study treatment. Listings of both adverse events associated with DBPCFC, and SAEs associated with DBPCFC, will be provided. A separate listing of all adverse events, sorted by time period of onset, will also be provided; and SAEs will be flagged.

An overall summary of frequencies of types of adverse events (TEAEs, SAEs, etc.) will be provided. An additional summary table of all TEAEs by Preferred Term, in order of descending frequency, will also be provided.

Summaries of adverse events by time period, SOC, and PT will be provided for TEAEs, treatment-emergent SAEs, and TEAEs related to study treatment. Subjects will be counted at most one time per time period overall, at most one time per SOC and at most one time per PT for these summaries. Summary tables will be sorted in order of time period (overall, then chronological), descending overall frequency of SOC and PT, with alphabetical sorting for ties. The number of subjects at risk for each time period (i.e., the number of subjects on study at the beginning of each time period) will be used as the denominator. In other words, the number of subjects in the Safety population will be used as the denominator for the Overall, On-treatment, and Post-Treatment time periods, the number of subjects undergoing Visit 01 will be used as the denominator for Visit 01, the number of subjects with 1+ updosing visits will be used as the denominator for Updosing Visit, the number of subjects undergoing the Exit DBPCFC will be used as the denominator for the Exit DBPCFC, Post-Exit DBPCFC time points.

Events related to study treatment are defined as those classified as possibly, probably, or definitely related to study treatment. If relationship is missing, the event will be conservatively be summarized as being related to study treatment.

Event severity is classified as mild, moderate, severe, life-threatening, or death. If severity is missing, a separate category of missing severity will be included in the summary table, and no imputation of severity will be performed.

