#### **10.5** Symptoms During DBPCFC

During each food challenge, the severity of pre-specified symptoms (hives, throat tightness, throat swelling, throat discomfort, hoarseness, laryngeal edema, skin flushing, pruritus, rhinorrhea, sneezing, nasal congestion, cough, wheezing, dyspnea, abnormal pain, abdominal cramping, nausea, vomiting) is rated as none, mild, moderate, severe, or life-threatening at each dose level of each food product. In addition, the presence of dose-limiting symptoms is recorded.

Symptoms at the Screening and Exit DBPCFCs will be listed by subject.

Symptoms will be summarized separately for symptoms during Screening DBPCFC (separately for the Safety and Screening DBPCFC Only populations) and Exit DBPCFC (for the Safety population). Subjects will be counted at most one time per symptom for each summary, at the most severe level recorded for that subject. The maximum dose severity of any symptom, and the presence of any dose limiting symptoms, will also be summarized.

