## **10.6** Symptoms During Escalation Dosing

During each escalation dosing, the severity of pre-specified symptoms is similarly rated as none, mild, moderate, severe, or life-threatening. In addition, the presence of dose-limiting symptoms and whether the dose was tolerated is recorded for each escalation dose.

Symptoms will be listed by subject, time point, and dose level. Maximum severity by symptom, maximum overall severity, and presence of any dose limiting symptoms will be summarized across all dose levels. Symptoms, maximum severity of any symptom, presence of dose limiting symptoms, and whether the dose was tolerated will be summarized for each dose level. If a subject is administered the same dose at more than 1 up-dosing visit (either the subject remained at the same dose as the previous visit, or a subject had a prior dose increase and subsequent dose reduction), the most severe symptoms and dose-limiting symptoms will be summarized for that dose level.

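### By the SAP's default denominator, Exit-challenge and per-dose symptom percentages divide by subjects who never had that challenge or dose, so they are diluted

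*SAP*

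**What the plan says.** SAP 6.6 gives the general rule: "Unless noted otherwise, the denominator for percentages will use the number of subjects in the analysis population". Three later sections describe symptom summaries.

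- **SAP 10.5** assigns the DBPCFC symptom summaries to populations: "separately for the Safety and Screening DBPCFC Only populations) and Exit DBPCFC (for the Safety population". Its counting rule is: "Subjects will be counted at most one time per symptom for each summary, at the most severe level recorded for that subject". It gives no denominator for the Exit table (14.3.4.4).
- **SAP 10.6** covers in-clinic escalation dosing. Symptoms, worst severity, dose-limiting symptoms and "whether the dose was tolerated will be summarized for each dose level" (Table 14.3.4.3, Safety). It gives no denominator for a dose level.
- **SAP 9.3.1** adds, for the Exit challenge: "The maximum symptom severity at each dose level, and the cumulative maximum severity at each dose level, will be summarized by treatment group" (Table 14.2.18, ITT). Again it gives no denominator.

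Elsewhere the SAP does depart from the default. For adverse events by time period, 10.3 says that "the number of subjects undergoing the Exit DBPCFC will be used as the denominator for the Exit DBPCFC" period, and 11.1 uses subjects at risk at each time point for epinephrine.

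On exposure, SAP Table 3.5 (footnote 6) limits the Exit DBPCFC to subjects who reached 300 mg and stayed on it for two weeks. The Safety and ITT populations (5.3, 5.4) require only that some randomized treatment was taken.

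**The concern.** A subject who never had the Exit challenge cannot contribute a symptom to the Exit table but still sits in its denominator. The same holds for a subject who never received a given up-dosing level or a given Exit challenge dose. The printed percentage then mixes how often people react with how many were exposed.

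This matters because the adverse event tables do not fill the gap. Protocol 7.1 sends allergic dosing symptoms to the Escalation Dosing form and clinic food-challenge reactions to study-specific forms, and challenge reactions reach the AE form only if serious. The symptom tables are therefore the main tabulation of non-serious challenge and in-clinic dosing reactions. Dosing symptoms belong to a secondary objective and a secondary safety endpoint (SAP 2.1.2, 2.3.2.2).

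**Working it through.** **Inputs from the documents.** About 50 subjects are randomized 1:1, so about 25 per arm. SAP 4 considers 3 or 5 subjects in each arm not undergoing the Exit DBPCFC. Its response rates among those challenged are 25% for placebo, and 66.7% (3 missing) or 70.75% (5 missing) for CPNA. Symptom rates are not given anywhere, so those below are assumptions.

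**1. The plan's own dilution.** Effective rate = rate among challenged × (25 − not challenged)/25.

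- 3 missing: placebo 0.25 × 22/25 = 22.0%; CPNA 0.667 × 22/25 = 58.7%.
- 5 missing: placebo 0.25 × 20/25 = 20.0%; CPNA 0.7075 × 20/25 = 56.6%.

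These match SAP 4. Counting the unchallenged as non-responders is deliberate for efficacy. For a symptom rate the same arithmetic applies, but a low value then looks favourable.

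**2. Exit symptom table (14.3.4.4).** The printed percentage is the true rate × 22/25 = 0.88, or × 20/25 = 0.80.

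| True rate among challenged (assumed) | 3 of 25 not challenged | 5 of 25 not challenged |
|---|---|---|
| 40% | 35% | 32% |
| 60% | 53% | 48% |
| 80% | 70% | 64% |

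The relative loss is 12% or 20%. In these scenarios it is the same in both arms.

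**3. Unequal non-challenge.** Assume 5/25 on CPNA and 1/25 on placebo are not challenged, with a true rate of 50% in both arms. The table prints 0.50 × 20/25 = 40% against 0.50 × 24/25 = 48%.

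**4. Exit severity by dose (14.2.18).** By Protocol 1.5, only subjects who tolerate 300 mg go on to 600 mg. Taking the 5-missing planning rates as the share given 600 mg (56.6% CPNA, 20% placebo), and assuming half of those dosed react in each arm, the table prints 0.5 × 56.6% = 28.3% against 0.5 × 20% = 10%. With the number dosed as denominator, both would read 50%. This needs no difference between arms in escalation failure.

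**5. Escalation by dose level (14.3.4.3).** If a fifth of an arm never reaches 300 mg and 20% of those who do have a given symptom (both assumed), the table prints 0.20 × 0.80 = 16%. The summary across all dose levels is not affected, because every Safety subject received at least one dose.

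**6. Peanut and oat in 10.5.** Severity is recorded "at each dose level of each food product", but the summaries are divided only into Screening and Exit. If the two foods were merged, a 60% peanut rate with an independent oat rate of 5% to 20% (assumed) would print as 1 − 0.40 × 0.95 = 62% to 1 − 0.40 × 0.80 = 68%. Merging can raise a rate or leave it unchanged; it cannot lower it.

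**The case against.** These are descriptive tables with no test or decision attached. Counts accompany percentages (SAP 6.6), dose levels administered at the DBPCFCs are summarized by food challenge and arm (9.3), and symptoms are listed by subject. A careful reader could largely recover the numbers exposed. The table shells are not in the documents and may print a suitable n. All of this stands, and it keeps the point modest. It does not remove it: the written rule is the population N, and where the SAP wants subjects at risk it says so.

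Three stronger readings are tempting, and the documents do not support them.

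- *CPNA symptoms are understated relative to placebo.* With a true 70% in both arms, and 3 or 5 CPNA but no placebo subjects unchallenged, CPNA would read 61.6% or 56.0% against 70%, an apparent advantage of 8 to 14 points. But SAP 4 puts the 3 or 5 in each arm, so both arms read 61.6% or 56.0% and the difference is zero. More non-challenge on CPNA is plausible: placebo capsules hold excipients only (Protocol 5.1), some moderate reactions to peanut OIT are expected (1.6.1), and repeated significant symptoms halt escalation (6.8.2). The documents do not quantify an imbalance. The 600 mg example runs the other way, against CPNA.
- *Unexposed subjects are recorded as symptom-free.* Nothing assigns them the severity category of none. They enter the denominator without a rating.
- *The SAP pools peanut and oat reactions and so understates rates.* Section 10.5 is silent on the split. Silence does not establish pooling, pooling would not understate, and escalation dosing involves no oat challenge.

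**Conclusion.** The denominator point holds. Following SAP 6.6 as written dilutes the percentages in Tables 14.3.4.4, 14.3.4.3 (by dose level) and 14.2.18. On the SAP's own scenarios, Exit symptom percentages lose a relative 12% or 20% in each arm; this rests only on about 25 per arm and 3 or 5 unchallenged.

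Distortion between arms arises where the share exposed differs, and its direction depends on which arm is less exposed. The 28% against 10% at 600 mg uses planning bounds (the minimum detectable CPNA rate and the maximum assumed placebo rate) and an assumed 50% reaction rate. The 40% against 48% for the whole challenge rests on an assumed imbalance. Neither is a forecast.

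The Safety-population screening tables are not materially affected, since randomized subjects had the screening challenge. The missing peanut/oat split in 10.5 is a secondary gap in specification that could blur attribution. The point should be corrected because these tables carry much of the safety description; it does not touch the primary efficacy analysis.

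**What to change.** In SAP 9.3.1, 10.5 and 10.6, state that the denominator is the number of subjects who received that challenge or that dose level, and print that n in each column. In 9.3.1, use those given the dose for severity at a dose. For cumulative severity, use those who started the challenge, because a worst severity so far remains defined after a subject stops.

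In 10.5, state that Tables 14.3.4.1, 14.3.4.2 and 14.3.4.4 show peanut and oat challenges separately, in line with the splits by food in Sections 9, 9.3 and 11.1. Food-specific n is needed especially for the Screening DBPCFC Only population, which admits subjects who had only one part of the challenge (5.7).

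The Completer population in the SAP addendum (2.2) does not solve this. It extends efficacy tables already produced on ITT, mITT and PP, whereas 14.2.18 is listed for ITT only and 14.3.4.3 and 14.3.4.4 are Safety tables.

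The cost is a few SAP sentences and changes to table shells. No new data are needed, since symptoms are already recorded by dose and food.
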